10 PHARMACOVIGILANCE

10.1 Terms and Definitions

The Medicines for Human Use (Clinical Trials) Regulations 2004 (SI 2004/1031) definitions:

Adverse Event (AE)

Any untoward medical occurrence in a subject to whom a medicinal product has been administered, including occurrences which are not necessarily caused by or related to that product.

Adverse Reaction (AR)

Any untoward and unintended response in a subject to an investigational medicinal product which is related to any dose administered to that subject.

Unexpected Adverse Reaction (UAR)

An adverse reaction the nature and severity of which is not consistent with the information about the medicinal product in question set out in the investigator's brochure.

Serious Adverse Event (SAE), Serious Adverse Reaction (SAR) or Suspected Unexpected Serious Adverse Reaction (SUSAR)

Any adverse event, adverse reaction or unexpected adverse reaction, respectively, that:

- results in death
- is life-threatening* (subject at immediate risk of death)
- requires in-patient hospitalisation or prolongation of existing hospitalisation**
- results in persistent or significant disability or incapacity, or
- consists of a congenital anomaly or birth defect
- other important medical events

*'life-threatening' in the definition of 'serious' refers to an event in which the patient was at risk of death at the time of the event; it does not refer to an event which hypothetically might have caused death if it were more severe.

**Hospitalisation is defined as an inpatient admission, regardless of length of stay, even if the hospitalisation is a precautionary measure for continued observation. Hospitalisations for a pre-existing condition, including elective procedures that have not worsened, do not constitute an SAE.

Other important medical events that may not result in death, be life-threatening, or require hospitalisation may be considered a serious adverse event/experience when, based upon appropriate medical judgment, they may jeopardise the subject and may require medical or surgical intervention to prevent one of the outcomes listed in this definition.

10.2 Notes on Adverse Event Inclusions and Exclusions

10.2.1 Include

- An exacerbation of a pre-existing illness
- An increase in frequency or intensity of a pre-existing episodic event/condition

- A condition (even though it may have been present prior to the start of the trial) detected after trial drug administration
- Continuous persistent disease or symptoms present at baseline that worsens following the administration of the study/trial treatment
- Treatment Emergent Signs and Symptoms (TESS) evaluation, to include the following specific signs and symptoms:
 - somnolence
 - increased excitability
 - mood swings
 - seizures (new presentation or exacerbation)*
 - rash
 - hypothermia
 - cough
 - other adverse effects not listed will also be documented; the Investigator's Brochure should be referred to when assessing causality and expectedness.

*A seizure diary will be given to the parents of those children who have an established diagnosis of epilepsy, whether or not they are receiving any antiepileptic medication (see Section 8.4.2).

Signs and symptoms will be graded and reported as; no symptoms (score 0); mild symptoms (score 1); moderate symptoms (score 2) and severe symptoms (score 3). Seriousness and causality will also be assessed by the reporting researcher (see section 10.3).

10.2.2 Do Not Include

- Medical or surgical procedures- the condition which leads to the procedure is the adverse event
- Pre-existing disease or conditions present before treatment that do not worsen
- Situations where an untoward medical occurrence has occurred e.g. cosmetic elective surgery
- Overdose of medication without signs or symptoms
- The disease being treated or associated symptoms/signs unless more severe than expected for the patient's condition.

10.3 Severity / Grading of Adverse Events

The assignment of the severity/grading should be made by the investigator responsible for the care of the participant using the definitions below.

Regardless of the classification of an AE as serious or not, its severity must be assessed according to medical criteria alone using the following categories:

Mild: does not interfere with routine activities

Moderate: interferes with routine activities

Severe: impossible to perform routine activities

A distinction is drawn between serious and severe AEs. Severity is a measure of intensity (see above) whereas seriousness is defined using the criteria in section 10.1, hence, a severe AE need not necessarily be a Serious Adverse Event.

10.4 Relationship to Trial Treatment

The assignment of the causality should be made by the investigator responsible for the care of the participant using the definitions in table 5.

If any doubt about the causality exists the local investigator should inform the study coordination centre who will notify the Chief Investigators. In the case of discrepant views on causality between the investigator and others, the MHRA will be informed of both points of view.

Table 5: Definitions of Causality

Relationship	Description
Unrelated	There is no evidence of any causal relationship. N.B. An alternative cause for the AE should be given
Unlikely	There is little evidence to suggest there is a causal relationship (e.g. the event did not occur within a reasonable time after administration of the trial medication). There is another reasonable explanation for the event (e.g. the participant's clinical condition, other concomitant treatment).
Possibly	There is some evidence to suggest a causal relationship (e.g. because the event occurs within a reasonable time after administration of the trial medication). However, the influence of other factors may have contributed to the event (e.g. the participant's clinical condition, other concomitant treatments).
Probably	There is evidence to suggest a causal relationship and the influence of other factors is unlikely.
Almost certainly	There is clear evidence to suggest a causal relationship and other possible contributing factors can be ruled out.

10.5 Expectedness

An AE whose causal relationship to the study drug is assessed by the investigator as "possible", "probable", or "almost certain" is an Adverse Drug Reaction.

All events judged by the investigator to be possibly, probably, or almost certainly related to the IMP, graded as serious and **unexpected** (see section 10.2 for list of Expected Adverse Events) should be reported as a SUSAR.

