8.4 Procedures for Assessing Safety

8.4.1 Expected Adverse Events (Treatment Emergent Signs and Symptoms [TESS])

Assessment of adverse effects will be undertaken weekly between weeks T0W to T12W. These reviews will be performed by the investigator at clinic attendance or the RP during home visits or via telephone assessment. Adverse effects will be assessed using Treatment Emergent Signs and Symptoms (TESS). The TESS evaluation will include the following specific signs and symptoms:

- somnolence (drowsiness)
- increased excitability
- mood swings
- seizures (new presentation or exacerbation)*

- rash
- hypothermia
- cough
- other adverse effects not listed will also be documented; the Investigator's Brochure should be referred to when assessing causality and expectedness.

*A seizure diary will be given to the parents of those children who have an established diagnosis of epilepsy, whether or not they are receiving any antiepileptic medication (see Section 8.4.2).

Signs and symptoms will be graded and reported as; no symptoms (score 0); mild symptoms (score 1); moderate symptoms (score 2) and severe symptoms (score 3). Seriousness and causality will also be assessed by the reporting researcher (see section 10).

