10.9 Responsibilities – MCRN CTU

The MCRN CTU is undertaking duties delegated to them by the trial sponsor, The Alder Hey Children's NHS Foundation Trust, and is responsible for the reporting of SUSARs and other SARs to the regulatory authorities (MHRA, competent authorities of other European member states in which the trial is taking place and, if required, the research ethics committees) as follows:

- SUSARs which are fatal or life-threatening must be reported not later than 7 days after the MCRN CTU is first aware of the reaction. Any additional relevant information must be reported within a further 8 days.
- SUSARs that are not fatal or life-threatening must be reported within 15 days of the MCRN CTU first becoming aware of the reaction.
- A list of all SARs (expected and unexpected) must be reported annually.

It is recommended that the following safety issues should also be reported in an expedited fashion

- An increase in the rate of occurrence or a qualitative change of an expected serious adverse reaction, which is judged to be clinically important;
- Post-study SUSARs that occur after the patient has completed a clinical trial and are notified by the investigator to the sponsor;
- New events related to the conduct of the trial or the development of the IMPs and likely to affect the safety of the subjects, such as:
 - a. A serious adverse event which could be associated with the trial procedures and which could modify the conduct of the trial;
 - b. A significant hazard to the subject population, such as lack of efficacy of an IMP used for the treatment of a life-threatening disease;
 - c. A major safety finding from a newly completed animal study (such as carcinogenicity).
 - d. Any anticipated end or temporary halt of a trial for safety reasons and conducted with the same IMP in another country by the same sponsor;
- Recommendations of the Data Monitoring Committee, if any, where relevant for the safety of the subjects.

Staff at the MCRN CTU will liaise with the Chief Investigator (or designated other specified in the protocol) who will evaluate all SAEs received for seriousness, expectedness and causality. Investigator reports of suspected SARs will be reviewed immediately and those that are SUSARs identified and reported to regulatory authorities and MREC. The causality assessment given by the Local Investigator at the hospital cannot be overruled and in the case of disagreement, both opinions will be provided with the report.

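### For the seven listed TESS terms, sections 10.5/10.2 and section 10.1 give different tests of expectedness, so a serious listed reaction worse than the Investigator's Brochure describes could be classed as expected

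*Protocol*

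**What the plan says.** Protocol section 10.1 calls a reaction unexpected when its "nature and severity of which is not consistent with the information about the medicinal product in question set out in the investigator's brochure". The SUSAR definition in the same section is built on that term, so both nature and severity count, and the Brochure is the yardstick.

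Section 10.5 is headed Expectedness and gives the rule the investigator applies. A reaction that is at least possibly related, serious and unexpected is to be reported as a SUSAR. For what is expected it says "see section 10.2 for list of Expected Adverse Events". It names neither the Brochure nor severity.

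The only list of specific events in section 10.2 is the TESS checklist in 10.2.1: somnolence, increased excitability, mood swings, "seizures (new presentation or exacerbation"), rash, hypothermia and cough. A closing bullet reads "other adverse effects not listed will also be documented; the Investigator's Brochure should be referred to when assessing causality and expectedness". The items are graded as "mild symptoms (score 1); moderate symptoms (score 2) and severe symptoms (score 3"), but no grade marks where an item stops being expected. Section 8.4.1 carries the same list under the heading "Expected Adverse Events (Treatment Emergent Signs and Symptoms [TESS"]).

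Section 10.8.1 makes unblinding at the trials unit depend on an event being judged unexpected. Section 10.9 sets 7 days for fatal or life-threatening SUSARs and 15 days for others. It then adds: "A list of all SARs (expected and unexpected) must be reported annually".

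**The concern.** Expectedness separates events that go to the regulator and ethics committee within days from those that appear in a yearly list. A protocol should therefore have one test for it. Here the definition uses the Brochure with a severity criterion, and the working rule points to a symptom checklist without one.

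The terms on the checklist matter in this population. Section 2.4.1 names seizures among the most significant theoretical risks, and mentions two spontaneous reports to the regulator and a survey describing increased or new seizures. Section 5.1 admits children with epilepsy. Section 2.2 says no serious side-effects have been reported, and describes reports of hypothermia as inconsistent. On the protocol's own account, a serious form of a listed event could go beyond what is already documented. The severity criterion in 10.1 exists to catch that case.

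**Working it through.** No figure is involved, so the check is a comparison of the rules. Take a reaction already judged serious and at least possibly related, and classify it under each rule.

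| Case | 10.1 (Brochure, nature and severity) | 10.5 read literally with 10.2 | Agree? |
|---|---|---|---|
| A. TESS term, consistent with the Brochure | Expected | Expected (on the list) | Yes |
| B. TESS term, different in nature or more severe than the Brochure | Unexpected, so a SUSAR | Expected (on the list) | **No** |
| C. Not a TESS term, consistent with the Brochure | Expected | Closing bullet refers to the Brochure: expected | Yes |
| D. Not a TESS term, not consistent with the Brochure | Unexpected, so a SUSAR | Closing bullet refers to the Brochure: unexpected | Yes |

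The rules part in case B only. The steps behind that row are:

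1. 10.5 sends the reader to a list of expected events in 10.2, and TESS is the only candidate there. The heading of 8.4.1 confirms that reading.
2. The entries for seizures and hypothermia have no limit on severity or seriousness. Severity is recorded on a scale up to 3, but the 10.5 rule does not use it.
3. The Brochure is mentioned in 10.2.1 and 8.4.1, but in the bullet on effects outside the list. Nothing there tells the reader to check a listed term against it.

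Consequences in case B:

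| Step | Under 10.1 | Under 10.5 read literally |
|---|---|---|
| Site to trials unit (10.7.2) | 24 hours | 24 hours |
| Unblinding at the trials unit (10.8.1) | Yes | No |
| Report to regulator and ethics committee if fatal or life-threatening (10.9) | 7 days | Annual list |
| The same, other serious (10.9) | 15 days | Annual list |

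The next step is whether the central review would catch the error. Section 10.9 has the Chief Investigator, or a designated other, evaluate each SAE for expectedness. It does not say against which document, so that reviewer has the same two rules to choose from. Section 10.9 also covers rate increases and qualitative changes in expected serious reactions, but expediting them is a recommendation and depends on a judgement of clinical importance.

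**The case against.** The case on the other side has real weight.

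- **10.1 is still in force.** It defines the SUSAR, and a parenthesis in 10.5 does not repeal it. This stands: an investigator who starts from 10.1 classifies correctly. It shows that the document contradicts itself, and does not show which rule a site will follow.
- **The Brochure is part of 10.2.** This stands for unlisted effects. A reader might infer that events in the Brochure but absent from the checklist would look unexpected. The closing bullet refers exactly those events to the Brochure, so the documents do not support that inference. The amendment log (section 18, version 5.0 to 6.1) points the same way on intent: items dropped from the checklist remain expected because they are in the Brochure.
- **Site errors can be corrected.** Every serious event reaches the trials unit within 24 hours, and expectedness is reassessed centrally. Only the local opinion on causality is protected from being overruled. This stands as mitigation. It is incomplete because the central review has no named reference.
- **The outcome depends on documents not at hand.** The Brochure was not available, nor was the reporting flowchart in 10.7. If the Brochure already describes seizures or hypothermia of the severity seen, the two rules agree (case A). This stands and makes the conclusion conditional.

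A reader might also infer that a serious seizure necessarily counts as expected and escapes expedited reporting. For the reasons above, the documents show only that it could.

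**Conclusion.** The point holds as an internal contradiction in the SUSAR rule: wrong as written, limited to the seven TESS terms. Sections 10.1 and 10.5/10.2 can classify the same related, serious, listed reaction differently.

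The affected event is a TESS term whose nature or severity goes beyond the Brochure. For such an event the literal reading of 10.5 replaces unblinding and a 7- or 15-day report with an entry in the annual list. The wait could at most approach 12 months. That upper bound requires three things together: the event exceeds the Brochure, the site follows 10.5 over 10.1, and the central review does not correct it. The documents give no rate for such events, so no expected number can be stated.

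The contradiction does not touch the randomisation, the endpoints or any efficacy estimate. It matters because it concerns which safety events in children are reported quickly, and because it is cheap to remove.

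**What to change.** 1. In 10.5, replace the reference to 10.2 with the Investigator's Brochure, judged by nature and severity as in 10.1.
2. In 10.2.1 and 8.4.1, state that TESS is a prompt for data collection and does not define expectedness, and that listed and unlisted events are both judged against the Brochure.
3. In 10.9, name the same reference for the central evaluation of expectedness.
4. Retitle 8.4.1 so that it no longer presents TESS as the expected events.
5. Check that the flowchart in 10.7 agrees.

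The cost is a few sentences and a heading, with possibly a few more expedited reports. No data collection changes.

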10.6 Follow-up After Adverse Events

All adverse events should be followed until satisfactory resolution or until the investigator responsible for the care of the participant deems the event to be chronic or the patient to be stable.

When reporting SAEs and SUSARs the investigator responsible for the care of the participant should apply the following criteria to provide information relating to event outcomes: resolved; resolved with sequelae (specifying with additional narrative; not resolved/ongoing; ongoing at final followup; fatal or unknown.

10.7 Reporting Procedures

All adverse events should be reported. Depending on the nature of the event the reporting procedures below should be followed. Any questions concerning adverse event reporting should be directed to the MCRN CTU in the first instance. A flowchart is given below to aid in determining reporting requirements.

[figure not shown]
10.7.1 Non serious ARs/AEs

All such events, whether expected or not, should be recorded on an Adverse Event eForm on the laptop. This laptop must then be connected to the Internet to ensure

that this data is transmitted to the MCRN CTU within seven days of the form being due.

10.7.2 Serious ARs/AEs/SUSARs

SARs, SAEs and SUSARs should be reported within 24 hours of the local site becoming aware of the event. The electronic SAE form asks for the nature of event, date of onset, severity, corrective therapies given, outcome and causality. The responsible investigator should sign (electronic signature) the causality of the event. The RP will need to connect their laptop to the server within 24 hours of becoming aware of the event in order to upload the information to the MCRN CTU. Daily reports will be generated from the eCRFs and will be checked daily by the Trial Co-ordinator via the Trial Management System. The local site should send any additional information within 5 days if the reaction has not resolved at the time of reporting. The MCRN CTU will notify the MHRA and main REC of all SUSARs occurring during the study according to the following timelines; fatal and life-threatening within 7 days of notification and non-life threatening within 15 days. All investigators will be informed of all SUSARs occurring throughout the study. Local investigators should report any SUSARs and /or SAEs as required by their Local Research Ethics Committee and/or Research & and Development Office.

10.8 Responsibilities - Investigator

The Investigator is responsible for reporting all AEs that are observed or reported during the study, regardless of their relationship to study product.

All SAEs must be reported within 24 hours by the investigator to the MCRN CTU on an SAE form unless the SAE is specified in the protocol or IB as not requiring immediate reporting. All other adverse events should be reported on the regular progress/follow-up reports.

Minimum information required for reporting:

- Study identifier
 - Study centre number
 - Randomisation number
 - A description of the event
 - Date of onset
 - Current status
 - Whether study treatment was discontinued
 - The reason why the event is classified as serious
 - Investigator assessment of the association between the event and study treatment
- i. The SAE eForm should be completed by the responsible investigator, the consultant named on the 'signature list and delegation of responsibilities log' who is responsible for the patient's care. The investigator should assess the SAE for the likelihood that that it is a response to an investigational medicine. In the absence of the responsible investigator the form should be completed and signed (digitally) by a designated member of the site trial team and submitted to the MCRN CTU. The responsible investigator should check the SAE form, make changes as appropriate, sign and then re-send to the MCRN CTU as soon as possible. The initial report shall be followed by detailed reports as appropriate.
 - ii. Staff at the institution must **notify** their local ethics committee (LREC) and their R and D department of the event (as per standard local procedure).
 - iii. In the case of an SAE the individual must be followed-up until clinical recovery is complete and laboratory results have returned to normal, or until the event has stabilised. Follow-up may continue after completion of protocol treatment if necessary.
 - iv. Follow-up information is noted on another SAE eForm and submitted to the MCRN CTU as information becomes available. Extra, annotated information and/or copies of test results may be provided separately.
 - v. The patient **must** be identified by randomisation number, date of birth and initials only. The patient's name **should not** be used on any correspondence.

10.8.1 Maintenance of Blinding

Systems for SUSAR and SAR reporting should, as far as possible, maintain blinding of individual clinicians and of trials staff involved in the day-to-day running of the trial. Unblinding clinicians may be unavoidable if the information is necessary for the medical management of particular patients. The safety of patients in the trial always takes priority. Seriousness, causality and expectedness should be evaluated as though the patient was on active drug. Cases that are considered serious, unexpected and possibly, probably or almost certainly related (i.e. possible SUSARs) would have to be unblinded at the clinical trials unit. Only those events occurring among patients on the active drug (unless thought to be due to the excipient in the

placebo) should be considered to be SUSARs requiring reporting to the regulatory authority and ethics committee.

